1 GLOSSARY OF TERMS

Names of test product(s)	Throughout this document, test product(s) will be referred to as [REDACTED] soft contact lenses [REDACTED] [REDACTED]
Name of Control Product(s)	CooperVision® BIORFINITY® soft contact lenses (Biofinity contact lenses or Biofinity)
Adverse Device Effect (ADE)	Adverse event related to the use of an investigational medical device (test product) or control product. Note: This definition includes adverse events resulting from insufficient or inadequate instructions for use, deployment, implantation, installation, or operation; any malfunction; and use error or intentional misuse of the test product or control product.
Adverse Event (AE)	Any untoward medical occurrence, unintended disease or injury, or untoward clinical signs (including abnormal laboratory findings) in subjects, users or other persons, whether or not related to the investigational medical device (test product). Note: For subjects, this definition includes events related to the test product, the control product, or the procedures involved. For users or other persons, this definition is restricted to events related to the test product. Requirements for reporting Adverse Events in the study can be found in Section 11.
Anticipated Serious Adverse Device Effect	Serious adverse device effect which by its nature, incidence, severity, or outcome has been identified in the risk management file.
Device Deficiency	Inadequacy of a medical device with respect to its identity, quality, durability, reliability, safety, or performance. Note: This definition includes malfunctions, use errors, and inadequate labeling.

	Requirements for reporting Device Deficiencies in the study can be found in Section 11.
Enrolled Subject	Any subject who signs an informed consent form for participation in the study.
Interventional Clinical Trial	A research trial that prospectively assigns, whether randomly or not, human participants or groups of humans to one or more health-related interventions to evaluate the effects on health outcomes, and/or a research trial in which diagnostic or monitoring procedures beyond standard of care are conducted and generate outcomes for use in analysis of data.
Investigational Product	Is defined as a preventative (vaccine), a therapeutic (drug or biologic), device, diagnostic, or palliative used as a test or control product in a clinical trial, including a product with a marketing authorization when used or assembled (formulated or packaged) in a way different from the authorized form, or when used for an unauthorized indication, or when used to gain further information about the authorized form.
Malfunction	Failure of a medical device to perform in accordance with its intended purpose when used in accordance with the instructions for use or clinical investigation plan.
Non-serious Adverse Event	Adverse event that does not meet the criteria for a serious adverse event.
Randomized Subjects	Any subject who is assigned a randomized treatment.
Serious Adverse Device Effect (SADE)	Adverse device effect that has resulted in any of the consequences characteristic of a serious adverse event.
Serious Adverse Event (SAE)	Adverse event that led to any of the following: 
 • Death.

	
• A serious deterioration in the health of the subject that either resulted in:
a. a life-threatening illness or injury. Note: Life-threatening means that the individual was at immediate risk of death from the event as it occurred, ie, it does not include an event which hypothetically might have caused death had it occurred in a more severe form.b. any potentially sight-threatening event or permanent impairment to a body structure or a body function.c. in-patient hospitalization or prolonged hospitalization. Note: Planned hospitalization for a pre-existing condition, without serious deterioration in health, is not considered a serious adverse event. In general, hospitalization signifies that the individual remained at the hospital or emergency ward for observation and/or treatment (usually involving an overnight stay) that would not have been appropriate in the physician's office or an out-patient setting. Complications that occur during hospitalization are adverse events. If a complication prolongs hospitalization or fulfills any other serious criteria, the event is serious. When in doubt as to whether "hospitalization" occurred, the event should be considered serious.d. a medical or surgical intervention to prevent a) or b).e. any indirect harm as a consequence of incorrect diagnostic test results when used within manufacturer's instructions for use.
--	---

	
• Fetal distress, fetal death, or a congenital abnormality or birth defect. 
Refer to Section 11 for additional SAEs.

Significant Non-Serious Adverse Event	
Is a symptomatic, device-related, non-sight threatening adverse event that warrants discontinuation of any contact lens wear for greater than or equal to 2 weeks.
 
Refer to Section 11 for additional Significant Non-Serious AEs.

Unanticipated Serious Adverse Device Effect	Serious adverse device effect which by its nature, incidence, severity or outcome has not been identified in the risk management file.
Use Error	Act or omission of an act that results in a different medical device response than intended by manufacturer or expected by user. Note: This definition includes slips, lapses, and mistakes. An unexpected physiological response of the subject does not in itself constitute a use error.

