10.2.4 Adverse Event Collection: Safety Assessment

Assess and record any AEs that are observed or reported, including those associated with changes in concomitant medication dosing since the previous visit. Requirements for reporting AEs in the study can be found in Section 11.

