11 ADVERSE EVENTS AND DEVICE DEFICIENCIES

11.1 General Information

An AE is any untoward medical occurrence, unintended disease or injury, or untoward clinical signs (including abnormal laboratory findings) in subjects, users, or other persons, whether or not related to the investigational medical device (test article). Refer to the Glossary of Terms and figures below for categories of AEs and SAEs.

Figure 11-1 Categorization of All AEs

[figure not shown]
[figure not shown]

Figure 11-2 Categorization of All SAE

SAEs

In addition to reporting all AEs (serious and non-serious) meeting the definitions, the Investigator must report any occurrence of the following as an SAE:

- An ocular infection including a presumed infectious ulcer with any of the following characteristics*:
 - Central or paracentral location
 - Penetration of Bowman's membrane
 - Infiltrates > 2 mm diameter
 - Iritis
 - Increase in intraocular pressure
 - Culture positive for microorganisms
 - Increasing size or severity at subsequent visits
- Any central or paracentral corneal event (such as neovascularization) that results in permanent opacification

- Hypopyon
- Hyphema
- Neovascularization within the central 6 mm of the cornea
- Permanent vision loss as defined by loss of 2 or more lines of BCVA from enrollment visit that fails to resolve
- Uveitis (anterior, intermediate, or posterior)
- Corneal abrasion affecting \geq 50% of corneal surface area

Significant Non-Serious AE

A significant non-serious AE is a device-related, non-sight threatening AE that warrants discontinuation of any contact lens wear for greater than or equal to 2 weeks. In addition, the Investigator must report any occurrence of the following as a Significant Non-Serious Adverse Event:

- Peripheral non-progressive non-infectious ulcers
- All symptomatic corneal infiltrative events
- Corneal staining score greater than or equal to Grade 3
- Temporary vision loss as defined by loss of 2 or more lines of BCVA from enrollment visit that persists for 2 or more weeks
- Neovascularization score greater than or equal to Grade 2

Device Deficiencies

A device deficiency is inadequacy of a medical device with respect to its identity, quality, durability, reliability, safety, or performance. A device deficiency may or may not be associated with subject harm (ie, ADE or SADE); however, not all ADEs or SADEs are due

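### Does the word symptomatic, present in the Glossary but absent from protocol 11.1, leave the significant non-serious AE flag in SAP 5.3.1 undefined?

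*Protocol*

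**What the plan says.** The category is defined in two places in the protocol.

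- **Glossary of Terms (Section 1):** "Is a symptomatic, device-related, non-sight threatening adverse event that warrants discontinuation of any contact lens wear" for at least 2 weeks. The entry ends with a pointer: "Refer to Section 11 for additional Significant Non-Serious AEs".
- **Section 11.1:** "A significant non-serious AE is a device-related, non-sight threatening AE that warrants discontinuation of any contact lens wear", again for at least 2 weeks. Five kinds of event follow that must always be reported in this category. They include "Peripheral non-progressive non-infectious ulcers" and "All symptomatic corneal infiltrative events"; the other three are a corneal staining grade, a neovascularization grade and a temporary loss of BCVA.

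The cross-references run both ways. The Glossary entry for adverse events says "Requirements for reporting Adverse Events in the study can be found in Section 11", and Section 10.2.4 says the same in its own terms ("Requirements for reporting AEs in the study can be found in Section 11"). The opening paragraph of Section 11.1 points back: "Refer to the Glossary of Terms and figures below for categories of AEs and SAEs".

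SAP 5.3.1 takes the definition of an AE from the protocol and says that significant non-serious ocular AEs will be marked. Its visible text does not define the category.

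**The concern.** One definition carries a restrictive condition that the other lacks. An investigator working from the Glossary would leave an asymptomatic event out of the category; one working from Section 11.1 would put it in. With about 8 sites, the same event could be classified in two ways, and the marker in the SAP 5.3.1 output would inherit the difference.

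Safety is part of the primary objective, and its assessment is entirely descriptive. Readers will rely on categories such as this one, so a category with two definitions deserves a check.

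**Working it through.** No arithmetic applies: the documents give no rate for these events and the SAP states no figure that depends on them. The check is a comparison of the two wordings.

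**Step 1. Shared criteria.** Both wordings require that the event be (a) related to the device, (b) not a threat to sight and (c) reason to stop lens wear for at least 2 weeks. The Glossary adds (d) symptomatic. Every event that meets the Glossary wording therefore also meets the Section 11.1 wording.

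**Step 2. Classify every non-serious event under each wording.**

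| Type of event | Glossary wording | Section 11.1 wording |
|---|---|---|
| On the mandatory list in 11.1 | In, through the pointer to Section 11 | In |
| Not listed, meets (a) to (c), symptomatic | In | In |
| Not listed, meets (a) to (c), asymptomatic | Out | In |
| Not listed, fails at least one of (a) to (c) | Out | Out |

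The wordings disagree in the third row only. An asymptomatic corneal infiltrate is the natural candidate, but it reaches that row only if it is device-related, warrants at least 2 weeks without lenses and does not already qualify through a listed item. Nothing in the documents shows that such a case would arise.

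**Step 3. Ask whether the text can be read as one definition.** The Glossary entry says that its own wording is not exhaustive and refers to Section 11 for further events. It names the section, not just the list inside it. Read that way, the category is the union of the two entries, and a third-row event is one of the additional events. The pointers to Section 11 for AE reporting, in the Glossary and in Section 10.2.4, fit this reading. No visible sentence states it, however.

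**Step 4. Trace a third-row event through the outputs.**

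- It is an AE under either wording, so the AE and Preferred Term counts stand. It is not serious under either wording, so the SAE count stands.
- It is device-related, hence an adverse device effect. Section 11.3 requires it on the corresponding eCRF within 24 hours, and the sponsor also assesses its causality.
- SAP 5.3.1 identifies relationship to lens in all AE tables and lists AEs by subject, with any that led to study discontinuation indicated.
- If it is a slit-lamp finding such as a corneal infiltrate, SAP 5.1 names it as a safety endpoint and SAP 5.3.2 reports it by eye.
- Only the marker for the category could differ. No separate incidence for this category appears in the visible SAP.

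**Step 5. Ask whether any inference depends on it.** Protocol 12.6 and SAP 5.2 state that there are no safety hypotheses.

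**The case for a change.** The best case for acting is that the dropped word is not idle. Section 11.1 itself uses symptom status to separate events: of the five listed items, only the one on infiltrative events carries it. AEs include clinical signs, which need no symptoms, and biomicroscopy at every scheduled visit looks for exactly such signs. The union reading can also be resisted. Section 11.1 restates the base definition and only then introduces its list as an addition, so the Glossary's pointer fits the list more naturally than a second base definition. And 11.1 sends readers back to the Glossary for categories, where they meet the narrower wording. The remedy would be a single edit.

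Much of this stands. The two entries differ in substance, and no visible sentence ranks them. What does not stand is the step from there to a consequence. No affected event is shown to be likely, and for any that did occur the sponsor would hold the full record through the 24-hour form and the listing, whichever wording the site had applied. The claim that nothing settles the matter is also less firm than the claim that the words differ: Figure 11-1 is not reproduced, the public protocol passes from 11.3 to 11.5, and part of SAP 5.3.1 is blacked out.

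**Conclusion.** This is a clerical slip with no demonstrated effect, and it does not call for a change to the plan. The wordings differ for one narrow class of event, whose number the documents do not let us estimate and which may be zero. For such an event the most that could change is its marker; no count, listing, endpoint or conclusion is shown to move.

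Two assumptions support this. First, the redacted part of SAP 5.3.1 contains no separate incidence or comparison built on this category; the visible text has none. Second, device-related events are documented as Section 11.3 requires, so that any disputed case can be identified from the data.

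The two protocol entries would read better if reconciled to one wording, and that can be done editorially whenever the text is next revised. This review takes no position on which wording is right, and the analysis does not depend on the choice.

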2 LIST OF ACRONYMS AND ABBREVIATIONS

Table 2-1

List of Acronyms and Abbreviations Used in This Protocol

Abbreviation	Definition
ADE	Adverse device effect
AE	Adverse event
BCVA	Best corrected visual acuity
Biofinity contact lens or Biofinity	CooperVision BIOFINITY (comfilcon A) soft contact lenses
CFR	Code of Federal Regulations
CLEAR CARE	CLEAR CARE Cleaning & Disinfecting Solution
CRF	Case report form
CSM	Clinical site manager
CTT	Clinical trial team
D	Diopter(s)
D/C	Discontinue
eCRF	Electronic case report form
EDC	Electronic data capture
FDA	US Food and Drug Administration
GCP	Good Clinical Practice
IB	Investigator's brochure
ICF	Informed consent form
ICH	International Council for Harmonisation of Technical Requirements for Pharmaceuticals for Human Use
IEC	Independent ethics committee
IP	Investigational product
IRB	Institutional review board
ISO	International Organization for Standardization
LID	Lens identification
logMAR	Logarithm of the minimum angle of resolution
mm	Millimeter
N/A	Not applicable
OD	Right eye
OS	Left eye
OU	Both eyes
SAE	Serious adverse event

Abbreviation	Definition
SADE	Serious adverse device effect
SiHy	Silicone hydrogel
SOP	Standard operating procedure
[REDACTED]	[REDACTED]
US / USA	United States of America
USAN	United States Adopted Name
USV	Unscheduled visit
VA	Visual acuity
vs	Versus

3 PROTOCOL SUMMARY

This will be a prospective, randomized [REDACTED] controlled, double-masked, parallel-group clinical study.

Approximately 8 sites in the US will enroll approximately 120 subjects. Subjects will be expected to attend 6 office visits: Screening / Baseline / Dispense, Week 1 Follow up, Week 2 Follow-up, Month 1 Follow-up, Month 2 Follow-up and Month 3 Follow up/Exit. The total expected duration of participation for each subject is approximately 3 months in this daily wear clinical study. Approximately 80 subjects will be assigned to wear the test lenses and 40 subjects will be assigned to wear the control lenses, [REDACTED]

Subjects and the study personnel conducting the study evaluations will be masked to treatment. Subjects who meet the inclusion and exclusion criteria will be randomized to wear either the test contact lenses [REDACTED] in both eyes or the control contact lenses (Biofinity) in both eyes for 3 months of daily wear exposure. [REDACTED]

[REDACTED]
[REDACTED]
[REDACTED]
[REDACTED]
[REDACTED]
[REDACTED]
[REDACTED].

At the Screening / Baseline / Dispense Visit, study lenses will be dispensed to qualified subjects [REDACTED]

All study lenses will be worn for at least 5 days per week and 8 hours per day in a daily wear modality (eg, will not be worn while sleeping). [REDACTED]

[REDACTED]
[REDACTED]
[REDACTED]

[REDACTED] Regardless of whether the subject is randomized to the test or the control group, CLEAR CARE® Cleaning & Disinfecting Solution (CLEAR CARE) must be used for cleaning and disinfection. [REDACTED]

Investigational product type	Medical Device
Study type	Interventional
Investigational products	Test Product: [REDACTED] soft contact lens Control Product: Biofinity soft contact lens
Purpose and rationale	The purpose of this clinical study is to demonstrate the performance of the investigational [REDACTED] soft contact lens compared to the commercially available Biofinity soft contact lens when worn in a daily wear modality, by assessing visual acuity as the primary variable.
Objective(s)	The primary objective is to demonstrate safety and effectiveness of the [REDACTED] soft contact lens when worn for daily wear as compared to the Biofinity soft contact lens.
Endpoint(s)	Primary Effectiveness 
Distance VA (Snellen) [REDACTED] [REDACTED] [REDACTED] [REDACTED] [REDACTED]

	
■ [REDACTED]
 
Safety
 
 • AEs • Biomicroscopy • Device deficiencies
Study Design	
This will be a prospective, randomized, [REDACTED] controlled, double-masked, parallel-group, daily wear clinical study. Subject participation in the study will be approximately 14 weeks with approximately 3 months of exposure to study lenses.

Subject population	
Volunteer subjects aged 18 or over who are adapted daily wear frequent replacement soft contact lens wearers, excluding Biofinity habitual wearers, have at least 3 months of soft contact lens wearing experience, and who wear their habitual lenses at least 5 days per week and at least 8 hours per day.
 
[REDACTED]
 
[REDACTED]
 
[REDACTED]
 
[REDACTED]
 
[REDACTED]

Key inclusion criteria (See Section 8.1 for a	
 • Successful wear of spherical daily wear frequent replacement soft contact lenses for distance correction in both eyes during the past 3 months for a minimum of 5 days per week and 8 hours per day.

complete list of inclusion criteria)	
 Manifest cylinder \leq 0.75 D in each eye
Key exclusion criteria (See Section 8.2 for a complete list of exclusion criteria)	
 Wearing habitual contact lenses in an extended wear modality (routinely sleeping in lenses for at least 1 night per week) over the last 3 months prior to enrollment. Monovision contact lens wearers Habitually wearing Biofinity lenses
Data analysis and sample size justification	
[REDACTED]
 
[REDACTED]
 
effectiveness and safety data will be presented separately based upon subject study status of Completed or Discontinued.
 
No formal hypotheses are formulated for the primary effectiveness endpoint, hence no inferential testing will be performed.
 
[REDACTED]
 
[REDACTED]
 
[REDACTED]
 
[REDACTED]
 
[REDACTED]
 
[REDACTED]

Key words	[REDACTED] Biofinity, daily wear, [REDACTED]
Associated materials	
CLEAR CARE Cleaning & Disinfecting Solution will be used for daily cleaning and disinfection.
 
[REDACTED]
 
[REDACTED]
 
[REDACTED]
 
[REDACTED]

Table 3-1 Schedule of Study Procedures and Assessments

Procedure/ Assessment	Visit 1 Screening/ Baseline/ Dispense	Visit 2 Week 1 Follow-up	Visit 3 Week 2 Follow-up	Visit 4 Month 1 Follow-up	Visit 5 Month 2 Follow-up	Visit 6 Month 3 Follow-up/Exit	Early Exit	USV
	Day 1	Day 7	Day 15	Day 30	Day 60	Day 95		
Informed Consent	✓	-	-	-	-	-	-	-
Demographics	✓	-	-	-	-	-	-	-
Medical History	✓	✓	✓	✓	✓	✓	✓	(✓)
Concomitant Medications	✓	✓	✓	✓	✓	✓	✓	(✓)
Inclusion/ Exclusion	✓	-	-	-	-	-	-	-
Habitual lens information (brand / manufacturer, modality, power, wear success, habitual lens care brand)	✓	-	-	-	-	-	-	-
[REDACTED]	█	█	█	█	█	█	█	█
[REDACTED]	█	█	█	█	█	█	█	█
[REDACTED]	█	█	█	█	█	█	█	█
[REDACTED]	█	█	█	█	█	█	█	█

Procedure/ Assessment	Visit 1 Screening/ Baseline/ Dispense	Visit 2 Week 1 Follow-up	Visit 3 Week 2 Follow-up	Visit 4 Month 1 Follow-up	Visit 5 Month 2 Follow-up	Visit 6 Month 3 Follow-up/Exit	Early Exit	USV
	Day 1	Day 7	Day 15	Day 30	Day 60	Day 95		
Biomicroscopy	✓	✓	✓	✓	✓	✓	✓	(✓)
Randomize	✓	-	-	-	-	-	-	-
IP Dispense	✓	✓	(✓)	(✓)	(✓)	-	-	(✓)
VA w/ study lenses (OD, OS Snellen distance) ¹	✓	✓	✓	✓	✓	✓	✓	(✓)

Printed By:

Print Date:

Procedure/ Assessment	Visit 1	Visit 2	Visit 3	Visit 4	Visit 5	Visit 6	Early Exit	USV
	Screening/ Baseline/ Dispense	Week 1 Follow-up	Week 2 Follow-up	Month 1 Follow-up	Month 2 Follow-up	Month 3 Follow-up/Exit		
	Day 1	Day 7	Day 15	Day 30	Day 60	Day 95		
1								
2								
3								
4								
5								
6								
7								
8								
9								
10								
11								
12								
13								
14								
15								
16								
17								
18								
19								
20								
21								
22								
23								
24								
25								
26								
27								
28								
29								
30								
31								
32								
33								
34								
35								
36								
37								
38								
39								
40								
41								
42								
43								
44								
45								
46								
47								
48								
49								
50								
51								
52								
53								
54								
55								
56								
57								
58								
59								
60								
61								
62								
63								
64								
65								
66								
67								
68								
69								
70								
71								
72								
73								
74								
75								
76								
77								
78								
79								
80								
81								
82								
83								
84								
85								
86								
87								
88								
89								
90								
91								
92								
93								
94								
95								
96								
97								
98								
99								
100								
101								
102								
103								
104								
105								
106								
107								
108								
109								
110								
111								
112								
113								
114								
115								
116								
117								
118								
119								
120								
121								
122								
123								
124								
125								
126								
127								
128								
129								
130								
131								
132								
133								
134								
135								
136								
137								
138								
139								
140								
141								
142								
143								
144								
145								
146								
147								
148								
149								
150								
151								
152								
153								
154								
155								
156								
157								
158								
159								
160								
161								
162								
163								
164								
165								
166								
167								
168								
169								
170								
171								
172								
173								
174								
175								
176								
177								
178								
179								
180								
181								
182								
183								
184								
185								
186								
187								
188								
189								
190								
191								
192								
193								
194								
195								
196								
197								
198								
199								
200								
201								
202								
203								
204								
205								
206								
207								
208								
209								
210								
211								
212								
213								
214								
215								
216								
217								
218								
219								
220								
221								
222								
223								
224								
225								
226								
227								
228								
229								
230								
231								
232								
233								
234								
235								
236								
237								
238								
239								
240								
241								
242								
243								
244								
245								
246								
247								
248								
249								
250								
251								
252								
253								
254								
255								
256								
257								
258								
259								
260								
261								
262								
263								
264								
265								
266								
267								
268								

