7 INVESTIGATIONAL PLAN

7.1 Study Design

This will be a prospective, randomized, [REDACTED] controlled, double-masked, parallel-group, daily wear clinical study.

This clinical study will engage approximately 8 clinic sites to enroll approximately 120 subjects with approximately 15 subjects per site.

Subjects will be expected to attend 6 office visits: Screening / Baseline / Dispense , Week 1 Follow-up, Week 2 Follow-up, Month 1 Follow-up, Month 2 Follow-up, and Month 3 Follow up/Exit. The total expected duration of participation for each subject is approximately 3 months in this daily wear study. Subjects will be randomized to wear either the test [REDACTED] contact lenses in both eyes or the control Biofinity contact lenses in both eyes.

[figure not shown]
Following randomization, study lenses will be dispensed to the subject [REDACTED]

[REDACTED]
[REDACTED]
[REDACTED]

Subjects will wear the lenses while awake in a daily wear modality. CLEAR CARE will be used for daily cleaning and disinfection. [REDACTED]

[REDACTED]
[REDACTED]

Figure 7-1 **Flowchart of Study Visits**

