8.1 Inclusion Criteria

Written informed consent must be obtained before any study specific assessment is performed. Upon signing informed consent, the subject will be considered enrolled in the study.

Subjects eligible for inclusion in this study must fulfill **all** of the following criteria:

1. At least 18 years of age and be able to understand and sign an IRB/IEC approved Informed Consent form.
2. Willing and able to attend all scheduled study visits as required per protocol.
3. Successful wear of spherical daily wear frequent replacement soft contact lenses for distance correction in both eyes during the past 3 months for a minimum of 5 days per week and 8 hours per day.
4. Manifest cylinder ≤ 0.75 D in each eye.

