8.3 Rescreening of Subjects

Rescreening of subjects is not allowed in this study.

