9.3 Treatment Assignment / Randomization

Subjects will be randomized in a 2:1 manner to receive either the [REDACTED] or Biofinity contact lenses, respectively. [REDACTED]
[REDACTED]

Only after signing the ICF, a subject will be assigned a subject number by the electronic data capture system.

[figure not shown]
[REDACTED]
[REDACTED]
[REDACTED]
[REDACTED]

[figure not shown]
[figure not shown]
At Visit 1, all eligible subjects will be randomized [REDACTED] to one of the treatment arms. [REDACTED]
[REDACTED]
[REDACTED]
[REDACTED]

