10.5 Discontinued Subjects

10.5.1 Screen Failures

Screen failures are subjects who were excluded from the study after signing the informed consent, not meeting the inclusion/exclusion criteria, and prior to randomization to product/dispense of study product.

The Investigator must document the reason for screen failure in the subject's case history source documents.

Subject numbers must not be re-used.

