1.2 Study Description

Key components of the study are summarized in Table 1-1.

Table 1-1 Study Description Summary

[figure not shown]
Study Design	Prospective, multi-center, randomized, [REDACTED] controlled, double-masked, parallel-group
Study Population	Volunteer subjects aged 18 or over who are adapted daily wear frequent replacement soft contact lens wearers, excluding Biofinity habitual wearers, have at least 3 months of soft contact lens wearing experience, and who wear their habitual lenses at least 5 days per week and at least 8 hours per day. [REDACTED] [REDACTED] [REDACTED] [REDACTED] [REDACTED] Target to complete: 90 subjects (60:30; Test:Control) Planned to enroll: ~120 subjects
Number of Sites	~8 (US)
Test Product	[REDACTED] soft contact lenses [REDACTED]
Control Product	CooperVision® BIOFINITY® (comfilcon A) soft contact lenses (Biofinity)
Duration of Treatment	Approximately 3 months
Visits	Visit 1: Screening/Baseline/Dispense (Day 1) Visit 2: Week 1 Follow-up Visit 3: Week 2 Follow-up Visit 4: Month 1 Follow-up Visit 5: Month 2 Follow-up Visit 6: Month 3 Follow-up/Exit

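### Does planning about 120 enrolled and about 80 + 40 assigned leave the trial short once screen failures are counted?

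*Protocol*

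**What the plan says.** The enrolment total appears three times. Protocol section 3 states that "Approximately 8 sites in the US will enroll approximately 120 subjects". Protocol section 7.1 repeats it by site: "enroll approximately 120 subjects with approximately 15 subjects per site". SAP Table 1-1 has "Planned to enroll: ~120 subjects", next to a target of 90 completers split 60 test and 30 control.

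The assigned numbers are in Protocol section 3: "Approximately 80 subjects will be assigned to wear the test lenses and 40 subjects will be assigned to wear the control lenses". They follow the 2:1 allocation in Protocol section 9.3 ("Subjects will be randomized in a 2:1 manner to receive either the").

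Enrolment has a single meaning. Protocol section 8.1 says: "Upon signing informed consent, the subject will be considered enrolled in the study". The Glossary, the All Enrolled set in Protocol section 12.2 and SAP section 2.1 agree, and the Glossary defines randomized subjects as a separate term. Section 10.5.1 places screening loss after that point ("Screen failures are subjects who were excluded from the study after signing the informed consent") and before randomization. Section 8.3 adds: "Rescreening of subjects is not allowed in this study".

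**The concern.** By the protocol's own definitions, a screen failure is enrolled but never assigned a lens. If about 120 are enrolled and about 120 are assigned, the figures leave no room for screening loss, although the protocol clearly expects some: it defines screen failures, keeps an Enrolled Not Dispensed analysis set, and does not let a failed subject return.

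The completer target seems to sharpen the point. The ratios 60/80 and 30/40 are both 75%, as if a 25% loss had been allowed for after assignment and nothing before it. If sites stopped at 120 consents, fewer than 80:40 would wear study lenses. With a 25% loss on top, completers would fall below 60:30, and the control arm is already the smaller one. In a trial meant to show safety and effectiveness from descriptive data, the numbers exposed and completing are the evidence.

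**Working it through.** **Inputs.** Planned enrolment of about 120, at about 8 sites with about 15 each (Protocol 3 and 7.1, SAP Table 1-1). Assigned 80 and 40 (Protocol 3). Allocation 2:1 (Protocol 9.3). Completers 90, as 60:30 (SAP Table 1-1). The screen-failure rate *s* is not in the documents, so it is an assumption, taken over 5% to 20%.

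**Reproducing the plan's figures.**

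- Sites: 8 × 15 = 120.
- Allocation: 120 × 2/3 = 80 and 120 × 1/3 = 40.
- Implied loss: 1 − 90/120 = 1 − 60/80 = 1 − 30/40 = 25%.
- Back again: 90/0.75 = 120, 60/0.75 = 80, 30/0.75 = 40.

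The arithmetic is exact. No visible text states the 25%; it is derived from these ratios.

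**If recruitment stopped at exactly 120 consents.** Assigned = 120(1 − *s*), split 2:1. The later loss that still leaves 90 completers is 1 − 90/assigned. Completers after a 25% loss = 0.75 × assigned. Consents needed to assign 120 = 120/(1 − *s*), rounded up.

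| Assumed *s* | Assigned (test:control) | Later loss that still leaves 90 | Completers after 25% loss | Consents to assign 120 |
|---|---|---|---|---|
| 0% | 120 (80:40) | 25% | 90 | 120 |
| 5% | 114 (76:38) | 21.1% | 85.5 | 127 |
| 10% | 108 (72:36) | 16.7% | 81 | 134 |
| 15% | 102 (68:34) | 11.8% | 76.5 | 142 |
| 20% | 96 (64:32) | 6.3% | 72 | 150 |

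**Reading SAP Table 1-1 by the definition of enrolled.** The table sets 120 enrolled beside 90 completing. If enrolled means consented, the 30 between them cover every loss after consent, screen failures included. For example, 10% screen failure followed by 15% dropout gives 120 × 0.90 × 0.85 = 91.8 completers (61.2:30.6), which meets the target.

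**Cost of a shortfall.** With the same spread and the same 2:1 split, a standard error grows as √(90/completers). With 81 completers this is √(90/81) = 1.05. With 72 it is √(90/72) = 1.12. No test or margin is attached to either figure.

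**The case for a change.** The best case for a change is that the contradiction lies in visible text and rests on the plan's own definitions. Enrolled and randomized are separate terms, so they should not carry the same count. The identical 75% ratio in each arm suggests that the allowance was meant for loss after assignment. A site told to enrol about 15 could reasonably count consents and stop early, and the clarification would cost a few words.

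The inconsistent use of the word stands, as does the consequence that exactly 120 consents would give fewer than 80:40 assigned. The rest is weaker:

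- **No cap.** Every enrolment total is approximate, and no visible rule ends recruitment at 120 consents. The ban on rescreening stops the same person from returning; it does not stop a site from consenting someone else. Approximate totals also absorb a few failures: 3 of 120 leaves 117 assigned (78:39).
- **No stated loss rate.** The 25% is an inference. The matching ratios make an allowance after assignment plausible, but no visible passage says so.
- **Two assumptions are needed.** Completers fall below 60:30 only if screening loss is added to the full 25% dropout.
- **Redaction.** Most of the sample-size row in Protocol section 3 is blacked out, so the visible text cannot show that screening loss was overlooked.

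**Conclusion.** No change follows. The plan uses *enrol* loosely where a count of subjects dispensed was probably meant. The stated figures are consistent with one another, and none is shown to be wrong beyond what *approximately* allows.

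Whichever way the 120 is counted, the analysis is the same. The Completed and Discontinued sets are drawn from Enrolled Dispensed (Protocol 12.2, SAP 2.4 and 2.5), so a screen failure cannot enter or distort them. Protocol 12.4.1.1 and SAP 4.2 and 5.2 set no hypotheses for the primary or safety endpoints, so a somewhat smaller number reduces descriptive precision only.

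The size depends on the unknown screen-failure rate and on recruitment ending strictly at 120 consents, which the documents do not require. Under that reading, 5% to 20% gives 76:38 down to 64:32 assigned, and 90 completers remain reachable while combined losses stay within 30. The harshest case examined, 20% followed by 25%, leaves 72 completers and standard errors about 12% larger. The judgement would differ if a power calculation or a decision rule rested on 80:40; none is visible.
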